12.5.1 Hypothesis Testing Strategy

The statistical hypothesis to be tested for the primary analysis with change in tumour size as the primary endpoint (defined in Section 10.7.6) is as follows:

- H₀: the mean best percentage change in the tumour size between the treatment groups are the same
- H_A: the mean best percentage change in the tumour size between the treatment groups are different

Since only two treatment groups are being tested there is no requirement for controlling the Family Wise Error Rate and the therefore multiplicity adjustments are not considered here.

12.5.2 Primary Estimand

The primary estimand attributes are given in Section 9.1. All analysis visits will be summarised using univariate statistics and a waterfall plot for the best percentage change from baseline will also be presented.

12.5.2.1 Imputation Methods

Imputation of missing target lesions will be performed using the scaling methods described in Section 10.7.3 and missing best percentage change from baseline will be imputed as described in Section 10.7.6.

Where analysis is performed on the ratio of postbaseline to baseline, zero values will be replaced with a constant equal to half of the smallest observed non-zero result across all patients (baseline and postbaseline).

No other imputation methods will be explored.

12.5.2.2 Primary Analysis

The primary efficacy analysis will evaluate the effect of setanaxib on the best percentage change in tumour size using an ANCOVA model, including covariates for treatment, baseline tumour size and the randomisation stratification HPV status (if there are at least 10 subjects at each level within each treatment group).

The number of patients, unadjusted mean, and adjusted least squares (LS) means for each treatment group will be presented, together with the difference in adjusted LS means, 80% and 95% CIs and corresponding p-value from the fitted ANCOVA model.

A plot of the residuals against the fitted values will be produced to check the assumption of constant variance. Any systematic effect in this residual plot along will indicate that a suitable transformation (log transformation) should be applied on the response of the model as appropriate to stabilise the variability of the error.

A normal probability plot will also be plotted of the residuals of the fitted ANCOVA model in addition to a Shapiro-Wilk test, used to test for the distribution of normality of the residuals. If the normal probability plot shows a concave curve of the residuals against the normal quantiles along with the p-value obtained from the Shapiro-Wilk test being less than 0.05, then this indicates a violation of the ANCOVA model assumption of the errors being normally distributed.

If the ANCOVA model assumptions are not upheld, logarithmic transformations on the response will be applied to normalise the data. The log(post-baseline) to log(baseline) ratio will be analysed using an ANCOVA model, including covariates for treatment, log-transformed baseline tumour size and the randomisation stratification HPV status.

The number of patients, unadjusted geometric mean, and adjusted geometric LS means for each treatment group will be presented, together with the difference in adjusted geometric LS means, 80% and 95% CIs and corresponding p-value from the fitted ANCOVA model.

The validity of the assumptions of the fitted transformed model will be checked similarly.

If the assumptions are not satisfied for the log-transformed model, a non-parametric method will be performed using a Ranked ANCOVA (Quade D. [1967]). A linear regression of the ranks of the best percentage change from baseline based on the ranks of the covariate for baseline tumour size and HPV status fitted as a class variable (ignoring treatment). The residuals from this regression model will then be analysed using an ANOVA model with treatment as the independent variable. The resulting p-value from the F test of this ANOVA will be reported.

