6.1 Changes from Protocol

6.1.1 Major Changes

• Initial Data Cut-Off for Primary Analysis

Section 8.1 of the protocol states the *"initial data cut-off will occur approximately 9 weeks after completion of enrolment, when all patients are expected to have had at least 3 cycles of pembrolizumab, at least one post-treatment scan, and the opportunity for a post-treatment tumour biopsy."*. During the preparation of this SAP a decision was made to extend this to approximately 15 weeks after completion of enrolment, with the aim for patients to have at least two post-treatment scans. This is clarified in Section 12.5 of this SAP.

Inclusion of the HPV Stratification Factor in Modelling

Section 8.4.2 of the protocol states the fitted analysis of covariance (ANCOVA) model as the only method to analyse the primary efficacy endpoint and without reference to human papillomavirus (HPV) status as a possible covariate. HPV status has been used as the stratification factor in the design of the study and not accounting for this factor in the analysis model may enhance the unexplained variability in the fitted linear model. Therefore, the HPV status will be included as a covariate in the ANCOVA model, if there are at least 10 patients at each level within each treatment group.

The same approach has been taken for the analysis of the cancer-associated fibroblasts (CAFs), cluster of differentiation 8 (CD8⁺), tumour-infiltrating lymphocytes (TILs) and the programmed cell death ligand 1 (PD-L1) expressions.

The HPV stratification factor, as well as the possible treatment-covariate interaction, have also been added as predictors for the Cox proportional hazards model described in Section 10.8.1 of this SAP.

• Duration of Response (DoR)

As DoR is a time-to-event endpoint, it was decided that an analysis using the Kaplan Meier method would be more appropriate than the Confidence Interval (CI) approach for a binomial proportion. This is described in Section 12.5.4.2 of this SAP.

• Supportive Analyses

Section 8.4.5 of the protocol describes a competing risk approach, using Fine & Gray (1999) methods to further analyse PFS. It was decided during the preparation of this SAP to remove this analysis from the scope of this SAP.

• Primary Estimand

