6.1.2 Minor Changes

- Section 8 of the protocol only discusses an estimand and intercurrent events related to the primary objective. The estimand framework has been built in Section 9.0 of this SAP for all the secondary objectives related to estimation of the treatment effect.
- Section 8.4.6 of the protocol describes a summary of abnormal physical examination findings should be presented. During the review of the initial SAP draft, the study team decided that a listing of all findings would be sufficient.
- Section 8.4.6 of the protocol also describes discrepancies between randomisation stratification information (obtained from IRT) and strata formed based on Screening factor collected on eCRFs (HPV status) will be explored. The HPV status on the CRF Randomisation page is integrated from the IRT data and so this presentation isn't necessary.
- Section 8.4.6 of the protocol also describes a presentation of modified World Health Organisation (WHO) ratings. These ratings are not collected for this study, hence no presentations will be provided.
- Section 8.2 of the protocol define the PK analysis set as "...all patients who receive at least 1 dose of setanaxib and have at least 1 measured concentration at a scheduled PK time point post-dose." A clarification was added to note that any concentration below the quantification limit (BQL) is considered to be a measured concentration and therefore included.

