12.5.3.1 Progression Free Survival (PFS)

The key secondary endpoint of PFS will be summarised by Kaplan-Meier plots presented by treatment group. The median, upper quartile, lower quartile PFS and the proportion of patients who are progression-free at 3, 6, and 12 months will be presented along with 80% Wald CIs, obtained using the Brookmeyer-Crowley method (1982). Patients who have not progressed by the time of the data cut-off will be censored following the rules defined in Section 10.8.1.

The comparison between the treatment groups of PFS will be performed by fitting a Cox proportional hazard model (Cox 1975) with treatment group, HPV status (if there are at least 10 patients in each HPV status within each treatment group) and the interaction term between treatment and HPV status (if statistically significant at the 5% level). Efron's method (1977) will be used to handle tied events in any of the independent event intervals. The covariate-adjusted hazard ratio between the treatment groups, based on the profile partial likelihood from the fitted Cox proportional hazards model, will be presented as a measure of the treatment effect along with the respective 80% and 95% Wald CIs and the asymptotic p-value from the Wald test for the difference in the covariate-adjusted log hazards in the fitted model.

If the interaction term between treatment and HPV status is statistically significant, the hazard ratio would be presented separately for HPV+ and HPV- along with the p-value of the interaction term and the 95% Wald CI based on the profile partial likelihood estimate for the interaction effect. Additionally, a Kaplan-Meier plot will be presented by treatment group and HPV status if there are at least 10 patients in each HPV status within each treatment group.

The proportionality of hazards will be examined for the fitted Cox proportional hazards model for PFS using Log-minuslog plots and Schoenfeld residuals. If the proportional hazard assumption is violated between the treatment groups, a modified max combo (Roychoudhury et al 2021) using the Fleming and Harrington 1981 weights (Fleming & Harrington 1981) such as FH(0,0), FH(0.5,0.5), FH(0,0.5), FH(0.5,0) will be implemented for estimating the performance of the competing treatment groups for PFS. The p-value obtained from each of the modified max combo tests will be reported.

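### The primary ANCOVA keeps HPV status, the only stratification factor, only if all four HPV-by-arm cells reach 10 patients; always including it is a small, near-free improvement

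*SAP*

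**What the plan says.** SAP 8.2 randomises 1:1, stratified by HPV status, and names no other factor. Protocol 8.4.2 did not include HPV in the primary model. SAP 6.1.1 adds it as a major change, on the ground that "not accounting for this factor in the analysis model may enhance the unexplained variability in the fitted linear model". It then makes the addition conditional: "HPV status will be included as a covariate in the ANCOVA model, if there are at least 10 patients", a count that must hold in all four HPV-by-arm cells. SAP 12.5.2.2 repeats this for the primary ANCOVA. Besides terms for baseline tumour size and treatment, it adjusts for "the randomisation stratification HPV status (if there are at least 10 subjects at each level within each treatment group".

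The two fallback models in 12.5.2.2 list HPV without the condition. The log-scale model uses "log-transformed baseline tumour size and the randomisation stratification HPV status". The ranked model regresses on "the ranks of the covariate for baseline tumour size and HPV status fitted as a class variable (ignoring treatment". The SAP does not name the analysis set in which the 10 patients are counted.

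**The concern.** A trial that stratifies on one factor would normally carry that factor into its primary model. Here, whether it does depends on how the HPV counts fall. SAP 6.1.1 states the cost of leaving HPV out, yet the condition allows exactly that. If the rule fails, the main model omits HPV. The fallback models, read literally, put it back, so a change of scale could also change the covariates.

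A requirement of 10 patients per cell suits an interaction term or separate subgroup estimates. A single binary main effect does not need it. At stake are a little precision and power, and a clear statement of which covariates the primary model contains.

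**Working it through.** **1. The plan's own power.** SAP 8.1 gives 25 per arm, a difference of 20 points, SD 30 and two-sided alpha 0.20. The noncentrality is 20 / (30 × √(2/25)) = 2.357. With 48 degrees of freedom, noncentral-t power is 85.4%, which agrees with the stated 85%.

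**2. When the rule is met.** Four cells of at least 10 mean at least 20 patients at each HPV level. With 50 patients that is 20 to 30 HPV-positive (40% to 60%). With 70 it is 20 to 50 (29% to 71%). The only HPV split in the documents is 20 positive and 36 negative in the phase 1b pembrolizumab study cited in Protocol 1.1.3, or 20/56 = 36%. I use it as an assumption. Selecting patients for a positive CAF level could shift the mix, because Protocol 1.2 links CAF-rich tumours to HPV-negative disease. Taking the HPV-positive count as binomial and splitting each stratum evenly between arms, the probability that the rule is met is:

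| HPV-positive share (assumed) | N=50 | N=60 | N=70 |
|---|---|---|---|
| 25% | 1% | 9% | 29% |
| 36% | 31% | 70% | 92% |
| 50% | 88% | 99% | 100% |

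The block size is not given. In simulation, permuted blocks of 4 reproduce the 36% row. Blocks of 6 give 27%, 65% and 89%.

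**3. Cost of always including HPV.** If HPV explains nothing, moving from 47 to 46 degrees of freedom changes power from 85.44% to 85.43%. Imbalance adds variance inflation of 1/(1 − r²), where r is the correlation between treatment and HPV:

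- HPV-positive counts of 6 v 4: r² = 0.25 × 0.08² / (0.20 × 0.80) = 0.0100, inflation 1.010, power 85.2%.
- HPV-positive counts of 2 v 4: r² = 0.25 × 0.08² / (0.12 × 0.88) = 0.0152, inflation 1.015, power 85.0%.

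The loss is at most about 0.4 point in these cases.

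**4. Gain.** This comes from a simulation of 60,000 trials per setting, with 25 per arm, 9 HPV-positive per arm, total SD 30 and true difference 20. Baseline tumour size is in both models (assumed to explain 5% of variance). The share explained by HPV is also assumed.

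| Variance explained by HPV | Power without / with HPV | Type I error without / with HPV | Mean 80% CI width without / with HPV |
|---|---|---|---|
| 0.8% | 86.3% / 86.4% | 19.6% / 19.8% | not recorded |
| 5% | 86.7% / 87.4% | 18.9% / 20.1% | 21.65 / 21.06 |
| 10% | 87.1% / 88.7% | 17.4% / 19.8% | 21.66 / 20.46 |
| 15% | 88.2% / 90.6% | 16.4% / 20.1% | 21.69 / 19.84 |

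The intervals narrow by 2.7%, 5.5% and 8.5% in the last three rows. Type I error without HPV falls below 20% because stratification already balances HPV between arms, while the unadjusted residual variance still contains it. With only 3 HPV-positive patients per arm, power was 86.2% in both models when HPV explained nothing, and 86.6% without v 87.4% with HPV at 5% of variance.

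**The case against.** The strongest case against is that this is preference rather than error. The rule is fixed in advance and depends only on counts, and leaving HPV out is conservative. Protocol 1.1.3 reports response of 25% v 19% by HPV status in one pembrolizumab study and similar rates across HPV subgroups in another. On that evidence the gain is 0.1 to 0.2 power point; the 5% to 15% range is an assumption. With 70 patients and 36% HPV-positive the rule is usually met. SAP 6.1.1 may also be meant to cover the fallback models. All of this stands, and it makes the point minor. It does not give a reason to keep the condition.

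A reader might infer three stronger things that do not hold.

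- **The primary test is biased or inflates type I error.** It does not: without HPV, simulated type I error is at or below 20%.
- **The Cox model for PFS should change too**, since SAP 12.5.3.1 also admits "HPV status (if there are at least 10 patients in each HPV status within each treatment group". There is no clear net gain. In simulation (38 events, hazard ratio 0.5), adding HPV raised power from 79.2% to 79.6% and Wald type I error from 19.8% to 20.7% when HPV had no effect. At an assumed HPV hazard ratio of 0.6, the rises were 77.4% to 79.0% and 19.3% to 21.1%. The median estimates, 0.51 without and 0.49 with HPV, lie about equally far from 0.50. A larger power gain (4.5 to 7 points) needs an HPV hazard ratio near 0.35, which the documents do not support with any figure. SAP 12.5.3.4 already plans the model without HPV.
- **The condition should go from every model that inherits the primary covariates.** The biomarker and site-subgroup models use smaller subsets whose balance stratification does not protect. With 10 per arm, the same standardised effect and HPV explaining nothing, power falls from 57.2% to 54.2% with HPV-positive counts of 5 v 2, and to 51.5% with 5 v 1. SAP 6.1.1 also says the same approach applies to CAFs, CD8+ and PD-L1, so little is unclear there beyond which patients are counted and whether FOXP3, which is not named, is covered.

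**Conclusion.** The point holds for the primary ANCOVA as a minor, optional improvement. With 50 patients the condition may well not be met: the probability of meeting it is 31% at 36% HPV-positive, but it runs from 1% to 88% over plausible shares, so whether HPV would in fact drop out cannot be predicted from the documents. If it does, the result remains valid but is somewhat conservative. The gain from always adjusting rests on assumed values for the variance explained by HPV and by baseline size. The near-zero cost at 25 per arm does not depend on the HPV share, provided HPV counts are close to balanced between arms, as stratified randomisation should ensure.

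**What to change.** Delete the 10-per-cell condition for the HPV main effect in the primary ANCOVA, in SAP 6.1.1 and 12.5.2.2. State that the main, log-scale and ranked models all adjust for HPV. This also removes the question of which patients are counted for the primary model. SAP 6.1.1 should then say separately that the condition still applies to the biomarker models, if that is intended.

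No new variable is needed: "The HPV status on the CRF Randomisation page is integrated from the IRT data".

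A count condition may stay for the treatment-by-HPV interaction, the HPV-specific Kaplan-Meier plots, and the biomarker and site-subgroup models. Changing the Cox main effect is optional.

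The cost is a wording change and one degree of freedom.

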8.4.4 Sensitivity Analysis

The proportionality of hazard will be examined in the sensitivity analysis for the fitted Cox proportional hazard model for PFS using the cumulative sums of martingale residuals for each treatment groups. The ASSESS statement with ODS Graphics in PROC PHREG step in SAS will perform this using both graphical and numerical methods of Lin, Wei, and Ying 1993 (Lin et al 1993). A violation of the proportional hazard assumption will indicate that the results obtained from the fitted Cox proportional hazard model will be invalid. In such circumstances, a modified max combo (Roychoudhury et al 2021) using the Fleming and Harrington 1981 weights (Fleming & Harrigton 1981) such as FH(0,0), FH(0.5,0.5), FH(0,0.5), FH(0.5,0) will be implemented for estimating the performance of the competing treatment groups for PFS. The p-value obtained from each of the modified max combo tests will be reported.

For each of the fitted ANCOVA models in the primary efficacy analysis and the secondary efficacy analyses, a plot of the residuals against the fitted values from the ANCOVA model will be produced to check for randomness in the plot. This is to check for the assumption of constant variance of the fitted model. Any systematic effect in this residual plot will indicate that a suitable transformation should be applied on the response of the model as appropriate to stabilise the variability of the error. A normal probability plot will also be plotted of the residuals of each of the fitted ANCOVA model to check if this fairly fits a straight line. Significant deviation from a straight line in this residual plot will indicate the violation of the ANCOVA model assumptions of the errors being normally distributed. In such cases, logarithmic transformations on the response will be applied, as appropriate, to normalise the data. The ANCOVA in such scenario will be fitted again on the log-normal response with log baseline values as the covariate, and the validity of the assumption of the fitted ANCOVA is the post-dose baseline ratio. If the assumptions

are not satisfied for the fitted transformed model, appropriate non-parametric method will be applied. Further details will be provided in the SAP.

The analysis of the primary endpoint will be repeated on the Per-Protocol Analysis Set to understand the effect of major protocol deviations on the treatment effect.

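### The SAP's normality check on the primary ANCOVA names only left-skewed residuals, which its log transform makes worse, and leaves out the right-skewed and S-shaped patterns

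*SAP*

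**What the plan says.** SAP 12.5.2.2 sets two checks on the primary ANCOVA.

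- **Constant variance**, from the plot of residuals against fitted values: "Any systematic effect in this residual plot along will indicate that a suitable transformation (log transformation) should be applied".
- **Normality**, from the normal probability plot and a test taken together: "If the normal probability plot shows a concave curve of the residuals against the normal quantiles", and Shapiro-Wilk must also give p<0.05. No other shape is named.

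The action is common to both: "If the ANCOVA model assumptions are not upheld, logarithmic transformations on the response will be applied to normalise the data". Then "The validity of the assumptions of the fitted transformed model will be checked similarly", and "If the assumptions are not satisfied for the log-transformed model, a non-parametric method will be performed using a Ranked ANCOVA". The ranked analysis reports only the p-value of an F test.

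Protocol 8.4.4 (v4.0) gives the normality criterion without a direction: "Significant deviation from a straight line in this residual plot will indicate the violation of the ANCOVA model assumptions". It follows the same order: transform, re-check, then a non-parametric method.

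SAP 12.5.2.3 plans no sensitivity analysis of the primary endpoint. The per-protocol repeat in SAP 12.5 changes the patients, not the rule.

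**The concern.** The trigger and the remedy point in opposite directions. The one normality pattern that the SAP names is the one a log transform aggravates, and the pattern a log transform is meant for is not named.

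This rule helps to decide which model gives the primary result, and whether that result is a difference in LS means, a geometric mean ratio, or a p-value alone. The model contains treatment, so its residuals can be examined only with treatment assignments in hand, after the soft lock described in SAP 12.0. If residuals are convex or S-shaped and Shapiro-Wilk rejects, an analyst who follows the text keeps a model that has failed its test. An analyst who departs from the text does so after unblinding.

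**Working it through.** **Step 1. What concave means on the stated axes.** Let r(z) be the residual plotted at normal quantile z. If r is concave, r(0) ≥ [r(−z) + r(z)]/2, so r(0) − r(−z) ≥ r(z) − r(0). The lower tail is longer than the upper, which is left skew. With the axes swapped the reading reverses. The SAP, however, puts residuals against quantiles.

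**Step 2. What the log does.** Take no change (ratio 1.0) as the centre.

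- A 30% fall (the partial-response threshold in protocol Appendix IV) and a 20% rise (the value imputed in SAP 10.7.6) lie 30 and 20 points away, a tail ratio of 30/20 = 1.5. On the log scale, ln 0.7 = −0.357 and ln 1.2 = 0.182, a tail ratio of 0.357/0.182 = 1.96. The left tail has grown.
- In the other direction, ratios 1/1.2 = 0.833 and 1.2 lie 16.7 points below and 20 above. On the log scale both distances are 0.182, so mild right skew disappears.

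A complete disappearance of target lesions stretches the left tail further, because on the ratio scale "zero values will be replaced with a constant equal to half of the smallest observed non-zero result across all patients".

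**Step 3. The plan's own design figure, for context.** With 25 per group, difference 20, SD 30 and two-sided alpha 0.20 (SAP 8.1), the non-centrality is 20/(30 × √(2/25)) = 2.357. The noncentral t with 48 df gives power 0.854, so the stated 85% is reproduced. The point does not depend on it.

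**Step 4. How often the rule fires.** Simulation of 4,000 trials per setting, 25 per arm, ANCOVA on treatment and baseline. Concave was taken as a negative quadratic coefficient of ordered residuals on normal quantiles. The log model used log(post/baseline) with log baseline as covariate. The distributions are assumptions: gamma errors with skewness ±1 and SD 30, a lognormal ratio with log-SD 0.35, a lognormal baseline, and change floored at −100%.

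| Errors | Plot concave | Shapiro-Wilk p<0.05 | SAP normality rule fires | Mean skewness, raw to log | Log model: Shapiro-Wilk p<0.05 |
|---|---|---|---|---|---|
| Normal | 49.2% | 4.1% | 2.0% | 0.01 to −1.28 | 72.1% |
| Left-skewed gamma | 99.1% | 58.3% | 58.3% | −0.70 to −2.19 | 98.3% |
| Right-skewed gamma | 0.9% | 62.2% | 0.1% | 0.80 to 0.03 | 4.1% |
| Lognormal ratio | 0.9% | 63.0% | 0.0% | 0.89 to 0.01 | 4.5% |

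Under left skew, 99.9% of the trials that trigger the rule fail the same check again on the log scale and so pass to ranked ANCOVA. Under right skew, the normality rule almost never fires although the log model would fit.

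**Step 5. The second route to the log.** A regression of squared residuals on fitted values, standing in for the visual variance check, was positive in 14.7% of the lognormal trials and 5.2% of the right-skewed gamma trials. The route exists but does not reliably make up for the normality rule.

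**Step 6. What it costs in inference.** Lognormal ratio, 25 per arm, 6,000 trials, alpha 0.20, power at a true ratio of 0.8:

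| Log SD | Type I error, untransformed | Power, untransformed | Power, log scale | Difference |
|---|---|---|---|---|
| 0.3 | 0.202 | 0.89 | 0.90 | 0.01 |
| 0.4 | 0.206 | 0.73 | 0.75 | 0.02 |
| 0.5 | 0.199 | 0.58 | 0.61 | 0.03 |

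A further simulation compared the SAP rule with a direction-free rule through the whole sequence (25 per arm, assumed distributions, normality route only). The conclusion at alpha 0.20 changed in about 3-10% of right-skewed trials, 3-5% of heavy-tailed trials, and 0% of left-skewed trials. Power rose by about 2-3 points under right skew and 5 under heavy tails. Type I error was 0.21-0.22 under the direction-free rule and 0.20-0.22 under the SAP rule.

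**The case against.** The best defence is that the rest of SAP 12.5.2.2 contains the damage, and most of that stands.

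- A reader might infer that the log is never applied where it would help. The text does not support that, because any systematic pattern in the residual-versus-fitted plot also leads to the log, and right-skewed multiplicative data can show one.
- A reader might infer that left-skewed data end on a scale that fits worse. They do not. The log model is re-checked and replaced by ranked ANCOVA, so the intermediate model is discarded.
- A reader might infer that keeping the untransformed model under right skew makes the primary test invalid. Type I error in Step 6 is close to 0.20, and the model keeps the LS mean difference that SAP 9.1.1 specifies.
- A reader might infer that the SAP made an undeclared change from the protocol. SAP 6.1 does not list one, but the SAP was written against protocol v5.0 and only v4.0 is available here. Protocol 8.4.4 v4.0 also defers further details to the SAP. Only the difference from v4.0 can be stated.
- The SAP sentence gives a sufficient condition and does not say that no other shape counts. That is a fair reading, but no other normality pattern is named, so a convex or S-shaped plot is left to judgement.

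None of this makes concave the right trigger for a log transform.

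**Conclusion.** The normality rule is wrong as written, and the consequence is modest. The direction of the error follows from the stated axes and needs no simulation. Its size does: about 2-3 points of power under right skew and about 5 under heavy tails, with no material effect on type I error and no change of conclusion under left skew. Those figures assume 25 per arm, the distributions above, and the normality route alone. Where the variance check also leads to the log, the loss is smaller.

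The other cost is procedural. The rule for choosing the primary model has to be followed in the wrong direction or overridden once treatment assignments are known.

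**What to change.** In SAP 12.5.2.2, replace the concave-curve condition in the normality sentence with: *departs from a straight line in any direction (convex, concave or S-shaped)*. Keep the joint Shapiro-Wilk condition. Keep the existing sequence: log model, re-check with the same direction-free rule, then ranked ANCOVA. Optionally, skip the log step when the curve is concave, since the final analysis is then the same.

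The cost is SAP wording before unblinding, with no new data or programs. One downside should be accepted openly: ranked ANCOVA, which gives a p-value without an estimate or interval, may be reached more often when residuals are S-shaped.
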